8.9 Evidence synthesis

We will pool the results across databases using random effect meta-analyses, I^2 for heterogeneity will be reported.

9. DATA MANAGEMENT

Note: Standard text will be generated on Data Management which will fit all studies run by the DARWIN EU[®] CC

10. QUALITY CONTROL

Note: This section will be automatically generated based on the DARWIN EU[®] Q/C processes, as detailed in a separate Deliverable 1.3.5.1)

11. LIMITATIONS OF THE RESEARCH METHODS

The study will be informed by routinely collected health care data that is available through existing governance and infrastructure and so data access and quality issues must be considered, and these will be documented to inform the HealthData@EU pilot. For example, cohorts of individuals with COVID-19 will be identified. However, outpatient tested positive cohorts will not capture all those individuals infected, given the variable availability of testing in outpatient settings. The inclusion of a study cohort identified by clinical diagnoses will address some of these limitations.

The included databases will vary in the data elements that they capture and in their current duration of follow-up. Depending on the dataset, not all study populations will be observed. For example, identifying the intensive services cohort will not be possible where inpatient hospital interventions are not observed. Similarly, not all outcomes may be available in all databases e.g. deaths. Some datasets may not capture COVID-19 diagnoses or tests occurring outside of hospital. Only the cohorts and outcomes that can reliably be identified will be assessed in the analyses. Since the vaccination programs changed over time (e.g. the primary vaccine courses targeted the general population, while the 4th dose were offered to more vulnerable people), the characteristics of patients receiving different doses may differ. However, we will stratify our analysis by prior vaccines whenever the power allows. It will also be assumed that vaccination recording is complete. Due to the availability of more recent data (CPRD is available until July 2022), some databases may have relative short follow-up time for study cohorts, and therefore may impact on the 90-days and 180-days incidence rates. The data elements that each data partner can provide will be detailed. The contextualisation of incidence rates using a historical background period assumes that coding practices and data recording are similar over time. However, this method has been used in previous studies focused on the 1st wave of covid, conducted by the same research group. [20,21] The analysis will calculate crude incidence rates and standardised incidence rates accounting for age and sex only. Differences in other potential confounders factors may exist and the characteristics of each cohort and stratification group will be inspected. No validation of outcomes using case note review will be performed.

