8.2 Study Setting and Data Sources

The selection of databases for this study was performed based on data reliability and relevance for the proposed research question among those databases onboarded and available within DARWIN EU. The selected databases fulfil the criteria required for the availability of key information on exposures, outcomes, and covariates, while covering different settings and regions of Europe.

Records on Covid-19 infection and vaccination (needed for objectives 2 to 5) will be available in all purposed databases except Estonia Biobank. We have previously published studies showing that these databases can generate reliable evidence on COVID-19 research. [20–22] Specifically, the availability of covid-19 tests results, and linked vaccination records through national/regional immunization program (SPRD, SIDIAP) increased the reliability of the identified study exposures. Inpatient admission and intensive care use (needed for objective 4) will be available in SIDIAP, which provides primary care records with linked hospitalization information.

Table 1. Description of the selected Data Sources.

Country	Name of Database	Justification for Inclusion	Health Care setting (e.g. primary care, specialist care, hospital care)	Type of Data (EHR, claims, registries)	Number of active subjects	Feasibility count of exposure (if relevant)	Feasibility count of disease (if relevant)	Data lock for the last update
Spain	SIDIAP	Complete records on SARS-CoV-2 infection, Covid-19 vaccination, and outcome events of interest; Include inpatient admission information. (objectives 1 to 5)	primary care database + linkage to hospital data	EHR	5.8M	Covid-19: 3865976, AstraZeneca :1152432, Janssen :257806, Pfizer :6548545, Moderna :3371395	VTE as example for all databases. 101966	1/6/2022
The UK	CPRD GOLD	Complete records on SARS-CoV-2 infection, Covid-19 vaccination,	primary care	EHR	3M	Covid-19: 360198, AstraZeneca	219844	07/2022

	Phase II C3-001 – Study Protocol	
	Author(s): [name], [name]	Version: v3.1
	Dissemination level: public	

Country	Name of Database	Justification for Inclusion	Health Care setting (e.g. primary care, specialist care, hospital care)	Type of Data (EHR, claims, registries)	Number of active subjects	Feasibility count of exposure (if relevant)	Feasibility count of disease (if relevant)	Data lock for the last update

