		and outcome events of interest (objectives 1 to 5, exclude 4b on worsening covid-19)				:2360815, Janssen :3034, Pfizer :2822947, Moderna :311069		
Germany	IQVIA Germany	Complete records on SARS-CoV-2 infection, Covid-19 vaccination, and outcome events of interest (objectives 1 to 5, exclude 4b on worsening covid-19)	outpatient visits of primary care physicians and a sample of specialists	EHR	8.5M	Covid-19:1723895, AstraZeneca :189261 , Janssen :83771 , Pfizer :2614482 , Moderna :428057	392674	1/9/2022
The Netherlands	IPCI	Complete records on SARS-CoV-2 infection, Covid-19 vaccination, and outcome events of interest (objectives 1 to 5, exclude 4b on worsening covid-19)	Primary care	EHR	1.39M	Covid-19: 941329, AstraZeneca :178192 , Janssen :19645 , Pfizer :1173104 , Moderna :463315	57087	1/12/2022

	Phase II C3-001 – Study Protocol	
	Author(s): [name], [name]	Version: v3.1
	Dissemination level: public	

Country	Name of Database	Justification for Inclusion	Health Care setting (e.g. primary care, specialist care, hospital care)	Type of Data (EHR, claims, registries)	Number of active subjects	Feasibility count of exposure (if relevant)	Feasibility count of disease (if relevant)	Data lock for the last update
Estonian	Estonian Biobank	Geographic representative (objective 1 only)	Biobank	EHR	0.2M	79411 (Covid-19)	25766	31/3/2021

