 - whether the vaccination record is 1st, 2nd, 3rd or 4th dose. A 21 day gap between two consecutive records of vaccine will be required to avoid repeated records of the same vaccine. The 21-days period was chosen based on the minimal recommended dosing schedule of the primary vaccine course in participated databases (Spain).
 - have at least 365 days of data availability prior to index date

Cohorts 2 to 5 will be stratified by prior COVID-19 infection status and for cohorts 2 to 4 also by prior SARS-CoV-2 vaccination status. All cohorts will additionally be stratified by whether patients are immunocompromised on the index date. People in each of the five cohorts will be required to have at least a year of observed history in the database prior to their index date. This is to ensure a sufficient time period to identify health conditions and medication use prior to individuals' index dates.

	Phase II C3-001 – Study Protocol	
	Author(s): [name], [name]	Version: v3.1
		Dissemination level: public

Table 3. Operational Definitions of Inclusion Criteria

Criterion	Details	Order of application	Assessment window	Care Setting ¹	Code Type	Diagnosis position ²	Applied to study populations:	Measurement characteristics/validation	Source for algorithm
Observation period of 365day prior entry (all 5 cohorts)	Study participants will be required to have 365 days prior history observed before contributing observation time	before	[-365,0]	n/a	n/a	n/a	All individuals within the selected databases	n/a	n/a
Covid-19 infection (cohort 2)	have either a positive test result for SARS-CoV-2 or a clinical diagnosis of COVID-19 on or after 1 st December 2021 (with the index date being whichever date comes first if both occur)	before	n/a	Primary care	SNOMED	n/a	All individuals within the selected databases	n/a	n/a
Covid-19 hospitalized (cohort 3)	a hospitalisation on or after 1 st December 2021 (with the index date the date of hospital admission), a record of a clinical diagnosis of COVID-19 or a positive test result for SARS-CoV-2 in the period between 3 weeks prior to and up to 3 days following the index date	before	[-21, 3]	Primary care, secondary care	SNOMED	n/a	All individuals within the selected databases	n/a	n/a

	Phase II C3-001 – Study Protocol	
	Author(s): [name], [name]	Version: v3.1
	Dissemination level: public	

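### IQVIA Germany is treated as having complete vaccination records, but Table 1's own counts (0.39 recorded vaccinations per active subject, against 1.32 to 1.95 elsewhere) make that implausible

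*Protocol*

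**What the plan says.** Section 8.2, Table 1, gives completeness of the infection, vaccination and outcome records as the reason for including IQVIA Germany, and assigns it to objectives 1 to 5 except 4b. Section 11 makes the same assumption for all databases: "It will also be assumed that vaccination recording is complete".

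The German row of Table 1 lists 8.5M active subjects and these vaccine counts: "AstraZeneca :189261 , Janssen :83771 , Pfizer :2614482 , Moderna :428057". The care setting given is outpatient primary care plus a sample of specialists. On linkage, section 8.2 says that "linked vaccination records through national/regional immunization program (SPRD, SIDIAP) increased the reliability of the identified study exposures"; the first acronym is presumably a misprint for CPRD. Neither IQVIA Germany nor IPCI is named there.

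The plan relies on vaccination status in several places. Section 8.5 says: "Cohorts 2 to 5 will be stratified by prior COVID-19 infection status and for cohorts 2 to 4 also by prior SARS-CoV-2 vaccination status". Sections 8.5 and 8.6.1 define the vaccinated cohort by brand and dose number. Section 8.8.3 makes prior vaccination a predictor in objective 4a, and section 8.8.5 makes it a stratifier of the incidence rate ratios and standardised ratios. Section 8.9 pools results across databases by random-effects meta-analysis.

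**The concern.** A person is placed in the stratum without prior vaccination because no vaccination record is found. That is sound only if a missing record means a missing vaccination. If one database captures a small part of the vaccinations given, its unvaccinated stratum is a mixture of unvaccinated people and people vaccinated without a record. A longer look-back, such as the abstract's requirement of visibility since 1 January 2020, cannot recover a vaccination that was never entered.

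The estimates at stake are the rates and ratios without prior vaccination (objectives 2 and 5) and the vaccination hazard ratio in objective 4a. Dose-number labels in cohort 5 are also exposed, because a later dose is labelled as an earlier one when a preceding dose is unrecorded. IQVIA Germany has the most active subjects in Table 1 (8.5M), so any artefact there enters the pooled estimates and the reported heterogeneity.

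**Working it through.** **1. Recorded vaccinations per active subject.** The Protocol states no such figure, so there is none to reproduce. All inputs are from Table 1. The SIDIAP row reads "5.8M Covid-19: 3865976, AstraZeneca :1152432, Janssen :257806, Pfizer :6548545, Moderna :3371395". For CPRD GOLD, the AstraZeneca count and the other brands are "2360815, Janssen :3034, Pfizer :2822947, Moderna :311069", with 3M active subjects.

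| Database | Sum of four brands | Active subjects | Ratio | Data lock |
|---|---|---|---|---|
| SIDIAP | 1,152,432 + 257,806 + 6,548,545 + 3,371,395 = 11,330,178 | 5.8M | 1.95 | 1/6/2022 |
| CPRD GOLD | 2,360,815 + 3,034 + 2,822,947 + 311,069 = 5,497,865 | 3M | 1.83 | 07/2022 |
| IPCI | 178,192 + 19,645 + 1,173,104 + 463,315 = 1,834,256 | 1.39M | 1.32 | 1/12/2022 |
| IQVIA Germany | 189,261 + 83,771 + 2,614,482 + 428,057 = 3,315,571 | 8.5M | 0.39 | 1/9/2022 |

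The German ratio is 0.39/1.95 = 20% of SIDIAP's and 0.39/1.32 = 30% of IPCI's.

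**2. Could something other than under-recording explain it?**

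- *Data lock.* Germany's is later than SIDIAP's and CPRD's, so an early lock is not the reason.
- *Denominator.* To match even IPCI, the German denominator would have to be 3,315,571/1.32 = about 2.5M rather than 8.5M.
- *Persons or records.* If the counts are records, each vaccinated person has at least one. If they are persons per brand, a person can appear under more than one brand. Either way at most 39% of active subjects have a record of a counted brand.

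**3. Make-up of the recorded-unvaccinated group.** Let c be true coverage (not in the documents, so assumed) and k the recorded doses per person with any record. Recorded coverage is r = 0.39/k, and the share of the recorded-unvaccinated who are in fact vaccinated is m = (c − r)/(1 − r).

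| Assumed c | k = 1 (r = 0.39) | k = 2 (r = 0.195) | k = 3 (r = 0.13) |
|---|---|---|---|
| 50% | 0.11/0.61 = 18% | 0.305/0.805 = 38% | 0.37/0.87 = 43% |
| 70% | 0.31/0.61 = 51% | 0.505/0.805 = 63% | 0.57/0.87 = 66% |
| 85% | 0.46/0.61 = 75% | 0.655/0.805 = 81% | 0.72/0.87 = 83% |

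The k = 1 column is the lower bound. The share passes one half when c exceeds about 70% (k = 1), 60% (k = 2) or 57% (k = 3).

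**4. Illustration for a hazard ratio.** Take a true vaccinated-versus-unvaccinated hazard ratio of 0.50 (arbitrary) and suppose that unrecorded vaccinees have the same risk as recorded ones. The observed ratio is about 0.50/((1 − m) + 0.50m). With m = 0.18, 0.51 and 0.75 this is 0.55, 0.67 and 0.80.

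**5. Do existing provisions catch it?** Section 11 limits analysis to cohorts and outcomes that can be reliably identified, but names no database and no test for vaccination, and Table 1 has already declared Germany complete. Table 8 restricts cohorts 2 to 5 to people with complete exposure information, which cannot reveal an unrecorded dose. No sensitivity analysis in Table 9 varies vaccination completeness or omits a database.

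**The case against.** The best defence is that Table 1 holds feasibility counts, not analysis data. Numerator and denominator are not strictly like for like: SIDIAP's Pfizer count (6,548,545) exceeds its 5.8M active subjects. The eligible cohorts need a year of history and, in the abstract, visibility since 1 January 2020, so recording among them may be better than across all 8.5M. Appendix I also lists an unspecified-vaccine concept for which Table 1 gives no count. That doses given outside the practice go unseen is an inference from the care setting. Completeness is openly listed as an assumption, incidence is reported for each database, and I² is reported, so a divergent German result would be visible.

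These points limit how precisely the problem can be sized. They do not reconcile a claim of complete records with a ratio of one fifth to one third of the others, and none of the reporting steps would keep the artefact out of the pooled figure.

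Four stronger readings are tempting, and the documents do not support them:

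- *The German unvaccinated stratum is mostly vaccinated people.* This needs coverage above about 57% to 70%, which the documents do not give. At 50% it does not follow.
- *The dose-number cohorts are largely mislabelled.* If a person's doses are all recorded or all missing, the recorded numbers are right. Only partial recording mislabels them, and nothing shows how common that is.
- *The vaccination effect is pulled toward the null.* That holds only if unrecorded vaccinees resemble recorded ones. Otherwise the direction is unknown.
- *All German vaccine results are compromised.* Objective 5 compares with the 2017–2019 background population. Brand-level rates and standardised ratios after a recorded dose do not need complete recording.

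**Conclusion.** The concern holds in limited form. On the Protocol's own counts, complete vaccination recording is implausible for IQVIA Germany, and the plan neither restricts nor tests the results that depend on it. The conflict itself needs no outside figure. Its size does: the lower bounds in step 3 rest on assumed coverage and on the 39% ceiling carrying over from all active subjects to the eligible cohorts.

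The estimates clearly affected are the German strata without prior vaccination and the German contribution to the objective 4a vaccination hazard ratio. Dose-number labels may be affected to an extent that cannot be computed. IPCI is a lesser question: it too has no claimed linkage, and has the lowest ratio of the other three databases despite the latest lock.

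**What to change.** - In Table 1, correct the German entry on completeness of vaccination records. In section 11, limit the completeness assumption to the linked sources, and correct the acronym in section 8.2 if CPRD is meant.
- Keep IQVIA Germany for objective 1, overall COVID-19 rates and standardised ratios, objective 4a without the vaccination term, and brand-level rates and standardised ratios after a recorded dose.
- Leave it out of the primary pooled strata without prior vaccination (objectives 2 and 5) and out of the pooled 4a vaccination hazard ratio.
- Add to Table 9 the dose-number pooled estimates with and without IQVIA Germany, and the pooled vaccination contrasts with and without IPCI.

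This costs Protocol wording and a few more pooled runs. The primary pooled vaccination contrasts would rest on SIDIAP, CPRD GOLD and IPCI, with slightly wider intervals.

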12. MANAGEMENT AND REPORTING OF ADVERSE EVENTS/ADVERSE REACTIONS

According to the new guideline on good pharmacovigilance practice (EMA/873138/2011 Rev 2*) there is no requirement for expedited reporting of adverse drug reactions from studies with secondary use of data (such as electronic health care databases).

13. GOVERNANCE BOARD ASPECTS

This document represents the views of the DARWIN EU[®] Coordination Centre only and cannot be interpreted as reflecting those of the European Medicines Agency or the European Medicines Regulatory Network.

	Phase II C3-001 – Study Protocol	
	Author(s): [name], [name]	Version: v3.1
	Dissemination level: public	

SIDIAP, IPCI, CPRD, EBB will require ethical approvals to perform this study. IQVIA DA Germany will not require any further specific approvals to undertake this study.

14. PLANS FOR DISSEMINATING AND COMMUNICATING STUDY RESULTS

Dissemination activities to be undertaken will include mainly, although not exclusively, the creation of a final report, scientific publications, and presentations at conferences.

15. OTHER ASPECTS

N/A

17. ANNEXES

Appendix I: List of Stand-Alone documents (e.g. lists with concept definitions (conditions & drugs))

Appendix II: ENCePP checklist for study protocols

	Phase II C3-001 – Study Protocol	
	Author(s): [name], [name]	Version: v3.1
		Dissemination level: public

	Phase II C3-001 – Study Protocol	
	Author(s): [name], [name]	Version: v3.1
	Dissemination level: public	

APPENDIX I – PRELIMINARY CONCEPTS FOR STUDY VARIABLES

APPENDIX I, TABLE 1: PRELIMINARY CONCEPTS FOR EXPOSURE

Exposures:

Concept Id	Concept name			domain
3661405	Acute bronchitis caused by SARS-CoV-2	COVID Diagnosis	Exposure	Condition
3655976	Acute hypoxemic respiratory failure due to disease caused by Severe acute respiratory syndrome coronavirus 2	COVID Diagnosis	Exposure	Condition
3661748	Acute kidney injury due to disease caused by Severe acute respiratory syndrome coronavirus 2	COVID Diagnosis	Exposure	Condition
3661406	Acute respiratory distress syndrome due to disease caused by Severe acute respiratory syndrome coronavirus 2	COVID Diagnosis	Exposure	Condition
3662381	Asymptomatic SARS-CoV-2	COVID Diagnosis	Exposure	Condition
756031	Bronchitis caused by COVID-19	COVID Diagnosis	Exposure	Condition
3656667	Cardiomyopathy due to disease caused by Severe acute respiratory syndrome coronavirus 2	COVID Diagnosis	Exposure	Condition
3656668	Conjunctivitis due to disease caused by Severe acute respiratory syndrome coronavirus 2	COVID Diagnosis	Exposure	Condition
439676	Coronavirus infection	COVID Diagnosis	Exposure	Condition
37311061	COVID-19	COVID Diagnosis	Exposure	Condition
4100065	Disease due to Coronaviridae	COVID Diagnosis	Exposure	Condition
3656669	Dyspnea caused by Severe acute respiratory syndrome coronavirus 2	COVID Diagnosis	Exposure	Condition
37310284	Encephalopathy due to disease caused by Severe acute respiratory syndrome coronavirus 2	COVID Diagnosis	Exposure	Condition
3661885	Fever caused by Severe acute respiratory syndrome coronavirus 2	COVID Diagnosis	Exposure	Condition
37310283	Gastroenteritis caused by SARS-CoV-2 (severe acute respiratory syndrome coronavirus 2)	COVID Diagnosis	Exposure	Condition
37310286	Infection of upper respiratory tract caused by Severe acute respiratory syndrome coronavirus 2	COVID Diagnosis	Exposure	Condition
3663281	Lower respiratory infection caused by SARS-CoV-2	COVID Diagnosis	Exposure	Condition
3661631	Lymphocytopenia due to Severe acute respiratory syndrome coronavirus 2	COVID Diagnosis	Exposure	Condition

37310287	Myocarditis due to disease caused by Severe acute respiratory syndrome coronavirus 2	COVID Diagnosis	Exposure	Condition
37310254	Otitis media due to disease caused by Severe acute respiratory syndrome coronavirus 2	COVID Diagnosis	Exposure	Condition
704995	Patient meets COVID-19 clinical diagnostic criteria	COVID Diagnosis	Exposure	Observation
700297	Patient meets COVID-19 laboratory confirmation criterion (detection of specific RNA in a clinical specimen using a molecular amplification detection test)	COVID Diagnosis	Exposure	Observation
704996	Patient meets COVID-19 laboratory diagnostic criteria	COVID Diagnosis	Exposure	Observation
700296	Patient meets COVID-19 presumptive laboratory evidence criteria (detection of specific antigen in a clinical specimen, OR detection of specific antibody in serum, plasma, or whole blood indicative of a new or recent infection)	COVID Diagnosis	Exposure	Observation
37016927	Pneumonia caused by Human coronavirus	COVID Diagnosis	Exposure	Condition
3661408	Pneumonia caused by SARS-CoV-2	COVID Diagnosis	Exposure	Condition
40479642	Pneumonia due to Severe acute respiratory syndrome coronavirus	COVID Diagnosis	Exposure	Condition
756039	Respiratory infection caused by COVID-19	COVID Diagnosis	Exposure	Condition
3655977	Rhabdomyolysis due to disease caused by Severe acute respiratory syndrome coronavirus 2	COVID Diagnosis	Exposure	Condition
3655975	Sepsis due to disease caused by Severe acute respiratory syndrome coronavirus 2	COVID Diagnosis	Exposure	Condition
320651	Severe acute respiratory syndrome	COVID Diagnosis	Exposure	Condition
37396171	Severe acute respiratory syndrome of upper respiratory tract	COVID Diagnosis	Exposure	Condition
37311060	Suspected COVID-19	COVID Diagnosis	Exposure	Observation
3661632	Thrombocytopenia due to Severe acute respiratory syndrome coronavirus 2	COVID Diagnosis	Exposure	Condition
45763724	Suspected coronavirus infection	COVID Diagnosis	Exposure	Observation
40218804	2019-ncov coronavirus, sars-cov-2/2019-ncov (covid-19), any technique, multiple types or subtypes (includes all targets), non-cdc	COVID19 positive test	Exposure	Measurement
40218805	Cdc 2019 novel coronavirus (2019-ncov) real-time rt-pcr diagnostic panel	COVID19 positive test	Exposure	Measurement
44789510	Coronavirus nucleic acid detection	COVID19 positive test	Exposure	Measurement

44811805	Coronavirus nucleic acid detection assay	COVID19 positive test	Exposure	Measurement
45770687	Coronavirus RNA (ribonucleic acid) detection assay	COVID19 positive test	Exposure	Measurement
44807536	Coronavirus RNA (ribonucleic acid) measurement by NAAT (nucleic acid amplification test)	COVID19 positive test	Exposure	Measurement
3667069	Detection of ribonucleic acid of Severe acute respiratory syndrome coronavirus 2 using polymerase chain reaction	COVID19 positive test	Exposure	Observation
36660491	Human coronavirus 229E RNA [Presence] in Lower respiratory specimen by NAA with non-probe detection	COVID19 positive test	Exposure	Measurement
36659667	Human coronavirus HKU1 RNA [Presence] in Lower respiratory specimen by NAA with non-probe detection	COVID19 positive test	Exposure	Measurement
36660329	Human coronavirus NL63 RNA [Presence] in Lower respiratory specimen by NAA with non-probe detection	COVID19 positive test	Exposure	Measurement
36660364	Human coronavirus OC43 RNA [Presence] in Lower respiratory specimen by NAA with non-probe detection	COVID19 positive test	Exposure	Measurement
742224	Infectious agent antigen detection by immunoassay technique, qualitative or semiquantitative, multiple-step method; severe acute respiratory syndrome coronavirus (eg, SARS-CoV, SARS-CoV-2 [COVID-19]) (Coronavirus disease [COVID-19])	COVID19 positive test	Exposure	Measurement
700360	Infectious agent detection by nucleic acid (DNA or RNA); severe acute respiratory syndrome coronavirus 2 (SARS-CoV-2) (Coronavirus disease [COVID-19]), amplified probe technique	COVID19 positive test	Exposure	Measurement
742218	Infectious disease (bacterial or viral respiratory tract infection), pathogen-specific nucleic acid (DNA or RNA), 22 targets including severe acute respiratory syndrome coronavirus 2 (SARS-CoV-2), qualitative RT-PCR, nasopharyngeal swab	COVID19 positive test	Exposure	Measurement
742219	Infectious disease (bacterial or viral respiratory tract infection), pathogen-specific nucleic acid (DNA or RNA), 22 targets including severe acute respiratory syndrome coronavirus 2 (SARS-CoV-2), qualitative RT-PCR, nasopharyngeal swab	COVID19 positive test	Exposure	Measurement
36661384	Influenza virus A and B and SARS-CoV-2 (COVID-19) and SARS-related CoV RNA panel - Respiratory specimen by NAA with probe detection	COVID19 positive test	Exposure	Measurement

36661375	Influenza virus A and B and SARS-CoV-2 (COVID-19) identified in Respiratory specimen by NAA with probe detection	COVID19 positive test	Exposure	Measurement
36661376	Influenza virus A and B RNA and SARS-CoV-2 (COVID-19) N gene panel - Respiratory specimen by NAA with probe detection	COVID19 positive test	Exposure	Measurement
705104	Measurement of Coronavirus (Coronavirinae subfamily species)	COVID19 positive test	Exposure	Measurement
705105	Measurement of Coronavirus (Coronavirinae subfamily species) antigen	COVID19 positive test	Exposure	Measurement
37310257	Measurement of Severe acute respiratory syndrome coronavirus 2 antigen	COVID19 positive test	Exposure	Measurement
756055	Measurement of Severe acute respiratory syndrome coronavirus 2 (SARS-CoV-2)	COVID19 positive test	Exposure	Measurement
586310	Measurement of Severe acute respiratory syndrome coronavirus 2 (SARS-CoV-2) Genetic material using Molecular method	COVID19 positive test	Exposure	Measurement
704991	Measurement of Severe acute respiratory syndrome coronavirus 2 (SARS-CoV-2) in Blood	COVID19 positive test	Exposure	Measurement
756029	Measurement of Severe acute respiratory syndrome coronavirus 2 (SARS-CoV-2) in Respiratory specimen	COVID19 positive test	Exposure	Measurement
586307	Measurement of Severe acute respiratory syndrome coronavirus 2 (SARS-CoV-2) in Saliva	COVID19 positive test	Exposure	Measurement
705107	Measurement of Severe acute respiratory syndrome coronavirus 2 (SARS-CoV-2) in Sample from nose	COVID19 positive test	Exposure	Measurement
704976	Measurement of Severe acute respiratory syndrome coronavirus 2 (SARS-CoV-2) in Sample from oropharynx	COVID19 positive test	Exposure	Measurement
586309	Measurement of Severe acute respiratory syndrome coronavirus 2 (SARS-CoV-2) in Specified specimen	COVID19 positive test	Exposure	Measurement
756065	Measurement of Severe acute respiratory syndrome coronavirus 2 (SARS-CoV-2) in Unspecified specimen	COVID19 positive test	Exposure	Measurement
702834	Measurement of Severe acute respiratory syndrome coronavirus 2 (SARS-CoV-2) specific cell-mediated immune response in Blood	COVID19 positive test	Exposure	Measurement
704992	Measurement of Severe acute respiratory syndrome coronavirus 2 (SARS-CoV-2) using Culture method	COVID19 positive test	Exposure	Measurement
705001	Measurement of Severe acute respiratory syndrome coronavirus 2 (SARS-CoV-2) using Nucleic acid amplification technique	COVID19 positive test	Exposure	Measurement

705000	Measurement of Severe acute respiratory syndrome coronavirus 2 (SARS-CoV-2) using Nucleic acid amplification technique in Blood	COVID19 positive test	Exposure	Measurement
756085	Measurement of Severe acute respiratory syndrome coronavirus 2 (SARS-CoV-2) using Nucleic acid amplification technique in Respiratory specimen	COVID19 positive test	Exposure	Measurement
586308	Measurement of Severe acute respiratory syndrome coronavirus 2 (SARS-CoV-2) using Nucleic acid amplification technique in Saliva	COVID19 positive test	Exposure	Measurement
705106	Measurement of Severe acute respiratory syndrome coronavirus 2 (SARS-CoV-2) using Nucleic acid amplification technique in Sample from nose	COVID19 positive test	Exposure	Measurement
704975	Measurement of Severe acute respiratory syndrome coronavirus 2 (SARS-CoV-2) using Nucleic acid amplification technique in Sample from oropharynx	COVID19 positive test	Exposure	Measurement
756084	Measurement of Severe acute respiratory syndrome coronavirus 2 (SARS-CoV-2) using Nucleic acid amplification technique in Unspecified specimen	COVID19 positive test	Exposure	Measurement
704993	Measurement of Severe acute respiratory syndrome coronavirus 2 (SARS-CoV-2) using Sequencing	COVID19 positive test	Exposure	Measurement
723477	SARS-CoV-2 (COVID-19) Ag [Presence] in Respiratory specimen by Rapid immunoassay	COVID19 positive test	Exposure	Measurement
706167	SARS-CoV-2 (COVID-19) N gene [Cycle Threshold #] in Unspecified specimen by NAA with probe detection	COVID19 positive test	Exposure	Measurement
706157	SARS-CoV-2 (COVID-19) N gene [Cycle Threshold #] in Unspecified specimen by Nucleic acid amplification using CDC primer-probe set N1	COVID19 positive test	Exposure	Measurement
706155	SARS-CoV-2 (COVID-19) N gene [Cycle Threshold #] in Unspecified specimen by Nucleic acid amplification using CDC primer-probe set N2	COVID19 positive test	Exposure	Measurement
715272	SARS-CoV-2 (COVID-19) N gene [Presence] in Nasopharynx by NAA with probe detection	COVID19 positive test	Exposure	Measurement
757678	SARS-CoV-2 (COVID-19) N gene [Presence] in Nose by NAA with probe detection	COVID19 positive test	Exposure	Measurement
706161	SARS-CoV-2 (COVID-19) N gene [Presence] in Respiratory specimen by NAA with probe detection	COVID19 positive test	Exposure	Measurement
586524	SARS-CoV-2 (COVID-19) N gene [Presence] in Respiratory specimen by Nucleic acid amplification using CDC primer-probe set N1	COVID19 positive test	Exposure	Measurement

586525	SARS-CoV-2 (COVID-19) N gene [Presence] in Respiratory specimen by Nucleic acid amplification using CDC primer-probe set N2	COVID19 positive test	Exposure	Measurement
36661378	SARS-CoV-2 (COVID-19) N gene [Presence] in Saliva (oral fluid) by NAA with probe detection	COVID19 positive test	Exposure	Measurement
586520	SARS-CoV-2 (COVID-19) N gene [Presence] in Serum or Plasma by NAA with probe detection	COVID19 positive test	Exposure	Measurement
706175	SARS-CoV-2 (COVID-19) N gene [Presence] in Unspecified specimen by NAA with probe detection	COVID19 positive test	Exposure	Measurement
706156	SARS-CoV-2 (COVID-19) N gene [Presence] in Unspecified specimen by Nucleic acid amplification using CDC primer-probe set N1	COVID19 positive test	Exposure	Measurement
706154	SARS-CoV-2 (COVID-19) N gene [Presence] in Unspecified specimen by Nucleic acid amplification using CDC primer-probe set N2	COVID19 positive test	Exposure	Measurement
723469	SARS-CoV-2 (COVID-19) ORF1ab region [Cycle Threshold #] in Respiratory specimen by NAA with probe detection	COVID19 positive test	Exposure	Measurement
706168	SARS-CoV-2 (COVID-19) ORF1ab region [Cycle Threshold #] in Unspecified specimen by NAA with probe detection	COVID19 positive test	Exposure	Measurement
723478	SARS-CoV-2 (COVID-19) ORF1ab region [Presence] in Respiratory specimen by NAA with probe detection	COVID19 positive test	Exposure	Measurement
723464	SARS-CoV-2 (COVID-19) ORF1ab region [Presence] in Unspecified specimen by NAA with probe detection	COVID19 positive test	Exposure	Measurement
586516	SARS-CoV-2 (COVID-19) [Presence] in Unspecified specimen by Organism specific culture	COVID19 positive test	Exposure	Measurement
723471	SARS-CoV-2 (COVID-19) RdRp gene [Cycle Threshold #] in Respiratory specimen by NAA with probe detection	COVID19 positive test	Exposure	Measurement
723470	SARS-CoV-2 (COVID-19) RdRp gene [Cycle Threshold #] in Unspecified specimen by NAA with probe detection	COVID19 positive test	Exposure	Measurement
706160	SARS-CoV-2 (COVID-19) RdRp gene [Presence] in Respiratory specimen by NAA with probe detection	COVID19 positive test	Exposure	Measurement
706173	SARS-CoV-2 (COVID-19) RdRp gene [Presence] in Unspecified specimen by NAA with probe detection	COVID19 positive test	Exposure	Measurement
586528	SARS-CoV-2 (COVID-19) RNA [Cycle Threshold #] in Respiratory specimen by NAA with probe detection	COVID19 positive test	Exposure	Measurement
586529	SARS-CoV-2 (COVID-19) RNA [Cycle Threshold #] in Unspecified specimen by NAA with probe detection	COVID19 positive test	Exposure	Measurement

715262	SARS-CoV-2 (COVID-19) RNA [Log #/volume] (viral load) in Unspecified specimen by NAA with probe detection	COVID19 positive test	Exposure	Measurement
706158	SARS-CoV-2 (COVID-19) RNA panel - Respiratory specimen by NAA with probe detection	COVID19 positive test	Exposure	Measurement
706169	SARS-CoV-2 (COVID-19) RNA panel - Unspecified specimen by NAA with probe detection	COVID19 positive test	Exposure	Measurement
723476	SARS-CoV-2 (COVID-19) RNA [Presence] in Nasopharynx by NAA with non-probe detection	COVID19 positive test	Exposure	Measurement
586526	SARS-CoV-2 (COVID-19) RNA [Presence] in Nasopharynx by NAA with probe detection	COVID19 positive test	Exposure	Measurement
757677	SARS-CoV-2 (COVID-19) RNA [Presence] in Nose by NAA with probe detection	COVID19 positive test	Exposure	Measurement
706163	SARS-CoV-2 (COVID-19) RNA [Presence] in Respiratory specimen by NAA with probe detection	COVID19 positive test	Exposure	Measurement
36661377	SARS-CoV-2 (COVID-19) RNA [Presence] in Respiratory specimen by Sequencing	COVID19 positive test	Exposure	Measurement
715260	SARS-CoV-2 (COVID-19) RNA [Presence] in Saliva (oral fluid) by NAA with probe detection	COVID19 positive test	Exposure	Measurement
715261	SARS-CoV-2 (COVID-19) RNA [Presence] in Saliva (oral fluid) by Sequencing	COVID19 positive test	Exposure	Measurement
723463	SARS-CoV-2 (COVID-19) RNA [Presence] in Serum or Plasma by NAA with probe detection	COVID19 positive test	Exposure	Measurement
706170	SARS-CoV-2 (COVID-19) RNA [Presence] in Unspecified specimen by NAA with probe detection	COVID19 positive test	Exposure	Measurement
723467	SARS-CoV-2 (COVID-19) S gene [Cycle Threshold #] in Respiratory specimen by NAA with probe detection	COVID19 positive test	Exposure	Measurement
723468	SARS-CoV-2 (COVID-19) S gene [Cycle Threshold #] in Unspecified specimen by NAA with probe detection	COVID19 positive test	Exposure	Measurement
723465	SARS-CoV-2 (COVID-19) S gene [Presence] in Respiratory specimen by NAA with probe detection	COVID19 positive test	Exposure	Measurement
586519	SARS-CoV-2 (COVID-19) S gene [Presence] in Serum or Plasma by NAA with probe detection	COVID19 positive test	Exposure	Measurement
723466	SARS-CoV-2 (COVID-19) S gene [Presence] in Unspecified specimen by NAA with probe detection	COVID19 positive test	Exposure	Measurement

586517	SARS-CoV-2 (COVID-19) whole genome [Nucleotide sequence] in Isolate by Sequencing	COVID19 positive test	Exposure	Measurement
757685	SARS-CoV+SARS-CoV-2 (COVID-19) Ag [Presence] in Respiratory specimen by Rapid immunoassay	COVID19 positive test	Exposure	Measurement
706172	SARS-like coronavirus N gene [Cycle Threshold #] in Unspecified specimen by NAA with probe detection	COVID19 positive test	Exposure	Measurement
706171	SARS-like coronavirus N gene [Presence] in Unspecified specimen by NAA with probe detection	COVID19 positive test	Exposure	Measurement
706166	SARS-related coronavirus E gene [Cycle Threshold #] in Unspecified specimen by NAA with probe detection	COVID19 positive test	Exposure	Measurement
586523	SARS-related coronavirus E gene [Presence] in Respiratory specimen by NAA with probe detection	COVID19 positive test	Exposure	Measurement
586518	SARS-related coronavirus E gene [Presence] in Serum or Plasma by NAA with probe detection	COVID19 positive test	Exposure	Measurement
706174	SARS-related coronavirus E gene [Presence] in Unspecified specimen by NAA with probe detection	COVID19 positive test	Exposure	Measurement
706159	SARS-related coronavirus+MERS coronavirus RNA [Presence] in Respiratory specimen by NAA with probe detection	COVID19 positive test	Exposure	Measurement
706165	SARS-related coronavirus RNA [Presence] in Respiratory specimen by NAA with probe detection	COVID19 positive test	Exposure	Measurement
723472	SARS-related coronavirus RNA [Presence] in Unspecified specimen by NAA with probe detection	COVID19 positive test	Exposure	Measurement
739902	SARS-COV-2 (COVID-19) vaccine, vector non-replicating	covid-19 vaccine	Exposure	drug
739903	SARS-COV-2 (COVID-19) vaccine, vector - Ad26 100000000000 UNT/ML	covid-19 vaccine	Exposure	drug
739905	SARS-COV-2 (COVID-19) vaccine, vector non-replicating Injectable Suspension	covid-19 vaccine	Exposure	drug
739906	SARS-COV-2 (COVID-19) vaccine, vector - Ad26 100000000000 UNT/ML Injectable Suspension	covid-19 vaccine	Exposure	drug
37003432	SARS-CoV-2 (COVID-19) vaccine, mRNA spike protein	covid-19 vaccine	Exposure	drug
37003433	SARS-CoV-2 (COVID-19) vaccine, mRNA-BNT162b2 0.1 MG/ML	covid-19 vaccine	Exposure	drug
37003435	SARS-CoV-2 (COVID-19) vaccine, mRNA spike protein Injectable Suspension	covid-19 vaccine	Exposure	drug
37003517	SARS-CoV-2 (COVID-19) vaccine, mRNA-1273 0.2 MG/ML	covid-19 vaccine	Exposure	drug

	Phase II C3-001 – Study Protocol	
	Author(s): [name], [name]	Version: v3.1
	Dissemination level: public	

37003518	SARS-CoV-2 (COVID-19) vaccine, mRNA-1273 0.2 MG/ML Injectable Suspension	covid-19 vaccine	Exposure	drug
37003436	SARS-CoV-2 (COVID-19) vaccine, mRNA-BNT162b2 0.1 MG/ML Injectable Suspension	covid-19 vaccine	Exposure	drug
